## 8.1.8 Administration

Uproleselan injection should be administered IV into a peripheral line, a central catheter, or a peripherally inserted central line catheter (PICC).

Infusion should take place at a steady rate over a period of 20 minutes (including flush if used) using a syringe pump or IV pump. Microbore tubing is preferred. In-line filtration (0.2 micron) is highly recommended.

Compatibility with other therapeutic agents has not been determined; therefore, uproleselan injection should be administered via a separate IV line and should not be administered concurrently with anything other than saline. If a flush is used, saline flush is preferred. The flush should be included in the 20 minute infusion.

## 8.1.9 Ordering

Individual sites will order uproleselan directly from GlycoMimetics, Inc.

#### 8.1.10 Accountability

The investigator, or a responsible party designated by the investigator, should maintain a careful record of the inventory and disposition of the agent using the NCI Drug Accountability Record Form (DARF) or another comparable drug accountability form. (See the NCI Investigator's Handbook for Procedures for Drug Accountability and Storage.)

#### 8.1.11 **Destruction and Return**

All participating centers will return unused uproleselan to GlycoMimetics, Inc. after the last participant enrolled has completed uproleselan.

#### 8.2 Busulfan

Injection (Busulfex®) NSC #750

#### 8.2.1 Description

Busulfan is a non-cell course specific bifunctional alkylating agent. In aqueous media, busulfan hydrolyzes to release methanesulfonate groups. This produces reactive carbonium ions that interact with cellular thiol groups and nucleic acids to form DNA

cross-links. Busulfan injection is 100% bioavailable by definition of intravenous administration. The elimination of busulfan appears to be independent of renal function, presumably reflecting the extensive metabolism of the drug in the liver, since less than 2% of the administered dose is excreted in the urine unchanged within 24 hours. The drug is metabolized by enzymatic activity to at least 12 metabolites, among which tetrahydrothiophene, tetrahydrothiophene 12 oxide, sulfolane, and 3-hydroxysulfolane were identified. These metabolites do not have cytotoxic activity. Irreversible binding to plasma proteins (primarily albumin) is approximately 32.4%. Busulfan has a plasma terminal elimination half-life (t1/2) of about 2.6 hours and demonstrates linear kinetics. It is rapidly distributed into tissue and crosses the blood-brain and the placental barriers. CSF concentrations are approximately equal to those in plasma. Itraconazole reduced busulfan clearance by up to 25% in patients receiving itraconazole compared to patients who did not receive itraconazole. Higher busulfan exposure due to concomitant itraconazole could lead to toxic plasma levels in some patients. Fluconazole had no effect on the clearance of busulfan.

#### 8.2.2 Form

Each ampoule or vial of busulfan injection contains 60 mg (6 mg/mL) of busulfan, N,N dimethylacetamide (DMA) 33% vol/vol and polyethylene glycol 400, 67% vol/vol.

## 8.2.3 Storage and Stability

Store refrigerated at 2°- 8°C, (36°- 46°F).

#### 8.2.4 **Compatibility**

Busulfan injection contains N,N-dimethylacetamide, which is incompatible with many closed-system transfer devices (CSTDs); the plastic components of CSTDs may dissolve and result in subsequent leakage and potential infusion of dissolved plastic into the patient.

#### 8.2.5 Handling

Qualified personnel, familiar with procedures that minimize undue exposure to themselves and the environment, should undertake the preparation, handling, and safe disposal of busulfan in a self-contained and protective environment.

#### 8.2.6 Availability

Commercially available from various manufacturers. See package insert for further information.

#### 8.2.7 **Preparation**

Dilute busulfan injection to a final concentration of approximately 0.5 mg/mL with NS or

D5W (the diluent quantity should be 10 times the volume of busulfan). The drug should not be infused with any other drug or IV solution other than NS or D5W. Always add the busulfan to the diluent, not the diluent to the busulfan injection. Mix thoroughly by inverting several times. Do not use polycarbonate syringes or filter needles with busulfan injection. Busulfan injection diluted in NS or D5W is stable at room temperature (25°C) for up to 8 hours but the infusion must be completed within that time. Busulfan injection diluted in NS is stable at refrigerated conditions 2°- 8°C (36°-46°F) for up to 12 hours but the infusion must be completed within that time. Busulfan 0.54 mg/mL solution in 0.9% sodium chloride injection was physically and chemically stable for 30 hours when stored in 50 mL polypropylene syringes at 2–8°C (36°-46°F) and protected from light. (Guichard N, et al. Am J Health-Syst Pharm. 2017; 74:1887-94)

## 8.2.8 Administration

Busulfan injection should be administered by IV infusion through a central venous catheter. Patients receiving busulfan in a conditioning regimen for bone marrow transplant must receive seizure prophylaxis with anticonvulsants (e.g., benzodiazepines, phenytoin, valproic acid or levetiracetam) to prevent seizures reported with the use of high dose busulfan. Administer anticonvulsants 12 hours prior to busulfan to 24 hours after the last dose of busulfan.

In dose-finding studies of busulfan where patients received concomitant busulfan and phenytoin, phenytoin reduced busulfan plasma AUC by approximately 15%. After an initial dose of busulfan injection, blood levels are monitored with bone marrow transplant patients in order to achieve a target area-under-the-curve (AUC) plasma concentration.

## 8.3 Clofarabine

(Cl-F-Ara-A, CAFdA, Clolar™, Evoltra®) NSC# 606869

## 8.3.1 **Description**

Clofarabine (2-chloro-9-[2'-deoxy-2'-fluoro-β-D-arabinofuranosyl]-9H-purine-6-amine) is a second-generation purine nucleoside analog designed as a hybrid molecule to overcome the limitations and incorporate the best qualities of fludarabine and cladribine. Clofarabine has several advantages over other nucleoside analogues: (1) increased resistance to deamination and phosphorolysis, hence better stability; (2) higher affinity to deoxycytidine kinase; (3) prolonged retention of the triphosphate compound in leukemic blasts; and (4) potent inhibition of DNA synthesis and of ribonucleotide reductase (RNR). Clofarabine is S-phase specific and cell cycle phase non-specific. Like other nucleoside analogs, clofarabine must be serially phosphorylated, first by deoxycytidine kinase and then by other kinases, to be active within cells. The primary cytotoxic effect of clofarabine is an inhibitor of both DNA polymerase and ribonucleotide reductase. These effects lead to depletion of intracellular deoxynucleotide triphosphate pools, and inhibition of DNA strands during synthesis. Clofarabine has been shown to disrupt the integrity of the mitochondrial membrane leading to the release of pro-

apoptotic mitochondrial factors and to programmed cell death. In addition to its antileukemic activity as a single agent, in vitro studies supported a role for clofarabine in biochemical modulation strategies to enhance the efficacy of other nucleoside analogs such as cytarabine. Clofarabine has been approved by the FDA for the treatment of pediatric patients with relapsed or refractory acute lymphoblastic leukemia (ALL) after at least two prior regimens.

The population pharmacokinetics of clofarabine were studied in 40 pediatric patients aged 2 to 19 years (21 males/19 females) with relapsed or refractory ALL or acute myelogenous leukemia (AML). At the given 52 mg/m^2 dose, similar concentrations were obtained over a wide range of BSAs. Clofarabine was 47% bound to plasma proteins, predominantly to albumin. Based on non-compartmental analysis, systemic clearance and volume of distribution at steady-state were estimated to be 28.8 L/h/m^2 and 172 L/m^2, respectively. The terminal half-life was estimated to be 5.2 hours. No apparent difference in pharmacokinetics was observed between patients with ALL and AML or between males and females. Based on 24-hour urine collections in the pediatric studies, 49-60% of the dose is excreted in the urine unchanged.

In vitro studies using isolated human hepatocytes indicate very limited metabolism (0.2%), therefore the pathways of non-renal elimination remain unknown. The pharmacokinetics of clofarabine have not been evaluated in patients with hepatic dysfunction. Reduce clofarabine starting dose by 50% in patients with CrCl of 30 to 60 mL/min. There is insufficient information to make a dosage recommendation in patients with CrCl less than 30 mL/min or in patients on dialysis.

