# Phase 2 Design

After completion of the phase 1 portion of the trial, enrollment at the recommended phase 2 dose will be expanded to bring total enrollment at this dose to 20 evaluable patients. Information about patients treated at the RP2D will be used to obtain preliminary estimates of drug exposure and efficacy, and to confirm safety. A one-stage stopping rule will monitor transplant-related mortality (TRM) for the 20 patients treated at the RP2D (see section 13.5).

Once the RP2D has been identified, an additional 14 to 17 evaluable patients will be enrolled at the RP2D. Interim monitoring of treatment related mortality (TRM) of the 20 patients treated at the RP2D (3 to 6 from Phase 1 and 14 to 17 from Phase 2) is described in section 13.5.

Treatment will be administered on an inpatient basis. Reported adverse events and potential risks are described in Section 7. Appropriate dose modifications are described in Section 6. No investigational or commercial agents or therapies other than those described below may be administered with the intent to treat the participant's malignancy.

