# 5.2.1 Administration of other Conditioning Agents

# **Fludarabine Administration**

Fludarabine will be administered 10 mg/m^2 IV daily as a 30 minute infusion for four days (-7 to -4). Patients with an estimated of GFR < 70 ml/min/1.73 m2 shall receive 8 mg/m2 IV daily. Dosing will be based on AIBW in patients whose actual weight exceeds 125% of their IBW (see formula in section 6.3). Duration of fludarabine infusion may be adjusted per institutional standards.

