# **Clofarabine Administration**

Clofarabine will be administered 30 mg/m2 IV daily as a 120 minute infusion for four days (-7 to -4). Dosing will be based on AIBW in patients whose actual weight exceeds 125% of their IBW (see formula in section 6.3). Doses will be administered immediately after completion of fludarabine infusion and just prior to start of uproleselan infusion. Duration of clofarabine infusion may be adjusted per institutional standards

Hydrocortisone 100 mg/m2/dose IV may be administered 30 minutes prior to each clofarabine dose for prevention of capillary leak syndrome.

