## 8.3.8 Administration

Infuse over 2 hours. May be infused over 1 hour or per institutional guidelines in some protocols, especially when lower doses are used. Continuous IV fluids are encouraged to decrease adverse events and tumor lysis effects. Consider prophylactic corticosteroids (see Treatment section) to prevent signs/symptoms of capillary leak syndrome or systemic inflammatory response syndrome (SIRS). Hypotension may be a sign of capillary leak syndrome or systemic inflammatory response syndrome (SIRS). Discontinue if the patient becomes hypotensive during administration; may consider therapy re-initiation with 25% dose reduction after return to baseline. An inline filter is not needed for administration. Do not administer any other medications through the same IV line.

Since clofarabine is primarily excreted through the kidneys, drugs with known renal toxicity should be avoided during clofarabine administration. In addition, since the liver is a known target organ for clofarabine toxicity, concomitant use of medications known to induce hepatic toxicity should be avoided.

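### Section 8.3.1 states a renal dose reduction for clofarabine that Sections 5.2.1 and 6 do not contain, in a clearance unit different from the one used for eligibility

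*Protocol*

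**What the plan says.** **Treatment plan.** Section 5.2.1 fixes the dose: "Clofarabine will be administered 30 mg/m2 IV daily as a 120 minute infusion for four days". The only dose adjustment there for clofarabine is the use of adjusted ideal body weight when actual weight is more than 125% of ideal. The same section does give a renal rule for fludarabine: patients with an estimated GFR below 70 mL/min/1.73 m2 "shall receive 8 mg/m2 IV daily" instead of 10 mg/m2.

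**Dose modifications.** Section 5.1 (Phase 2 Design) states: "Appropriate dose modifications are described in Section 6". Section 6 covers tacrolimus, methotrexate and obesity, and rules out changes to uproleselan. Apart from the obesity weight rule in 6.3, it says nothing about clofarabine.

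**Pharmaceutical information.** Section 8.3.1 says: "Reduce clofarabine starting dose by 50% in patients with CrCl of 30 to 60 mL/min". For lower clearance it says: "There is insufficient information to make a dosage recommendation in patients with CrCl less than 30 mL/min or in patients on dialysis". Section 8.3.8 directs that the drug be stopped if hypotension occurs during administration, and adds that the team "may consider therapy re-initiation with 25% dose reduction after return to baseline".

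**Eligibility.** Section 3.2.10 excludes an estimated GFR below 60 mL/min/1.73 m2, requires radionuclide testing when the equations give less than 90, and does not accept a 24-hour urine creatinine clearance in its place. Patients may weigh as little as 10 kg (3.1.3).

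**The concern.** A site that follows 5.2.1 and Section 6 would give 30 mg/m2 whatever the clearance. A site that follows 8.3.1 would give half of that to a patient in the 30 to 60 mL/min band. The protocol does not say which section prevails.

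The unit makes this harder to settle. The rule is in mL/min and names CrCl without a method, while the trial's other renal thresholds are indexed to 1.73 m2 of body surface. In a trial that admits 10 kg children, the two units give very different answers for the same kidneys.

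Clofarabine is part of the backbone on which uproleselan is assessed, without a comparator, in 20 patients at the recommended phase 2 dose. Evaluability (13.1.1 and 13.1.2) depends on uproleselan doses only, so a patient given reduced clofarabine would still count in the DLT and efficacy analyses.

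**Working it through.** The plan gives no figure on this point to reproduce. The check is a unit conversion.

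**Inputs from the protocol:** band of 30 to 60 mL/min (8.3.1); exclusion below 60 mL/min/1.73 m2 (3.2.10); minimum weight 10 kg (3.1.3); dose 30 mg/m2 (5.2.1).

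**Assumptions, not in the protocol:** CrCl equal to GFR; normal indexed GFR of 90 to 140; heights as shown for each weight; BSA by the Mosteller formula, √(kg × cm / 3600).

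**Indexed reading.** Values below 60 are excluded, so at enrollment only a value of exactly 60 lies in the band. Otherwise the rule could be met only by a fall after enrollment.

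**Literal reading.** Absolute clearance = indexed GFR × BSA / 1.73.

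At BSA 0.7 m2:
- indexed 90: 90 × 0.7 / 1.73 = 36 mL/min
- indexed 120: 120 × 0.7 / 1.73 = 49 mL/min
- indexed value that gives 30 mL/min: 30 × 1.73 / 0.7 = 74
- indexed value that gives 60 mL/min: 60 × 1.73 / 0.7 = 148

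Absolute clearance in mL/min for example children:

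| Weight, assumed height | BSA (m2) | Indexed 90 | Indexed 100 | Indexed 120 | Indexed 140 |
|---|---|---|---|---|---|
| 10 kg, 80 cm | 0.47 | 24.5 | 27.2 | 32.7 | 38.1 |
| 12 kg, 86 cm | 0.54 | 27.9 | 30.9 | 37.1 | 43.3 |
| 15 kg, 98 cm | 0.64 | 33.2 | 36.9 | 44.3 | 51.7 |
| 20 kg, 115 cm | 0.80 | 41.6 | 46.2 | 55.4 | 64.7 |
| 25 kg, 127 cm | 0.94 | 48.9 | 54.3 | 65.1 | 76.0 |
| 30 kg, 137 cm | 1.07 | 55.6 | 61.8 | 74.1 | 86.5 |

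Three results follow:
- At indexed 120, the children from 10 to 20 kg lie in the 50% band and the 25 kg child does not. At indexed 90, the band runs from the 15 kg child to the 30 kg child.
- At indexed 90, the 10 kg and 12 kg children lie below 30 mL/min, as does the 10 kg child at indexed 100. There 8.3.1 gives no dose at all.
- For the 15 kg child (unrounded BSA 0.639), 30 mg/m2 is 30 × 0.639 = 19.2 mg per dose; half is 9.6 mg.

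**The case against.** **Section 8 is general product information.** The sentence stands in a drug description that also quotes pharmacokinetics at 52 mg/m2, which is not this trial's dose. For fludarabine, Section 8.4.1 makes a general remark on renal adjustment and the working rule is in 5.2.1. Clofarabine may be meant to follow the same pattern. This reading is plausible, but the protocol does not state it. The tacrolimus and methotrexate entries (8.5.7 and 8.6.8) refer the reader to Sections 5 and 6. Section 8.3.1 has no such reference on dose, and 5.2.1 has no matching clofarabine rule.

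**Section 6 is not exhaustive.** The fludarabine renal rule and the busulfan adjustment guided by pharmacokinetics are both in 5.2.1. Absence from Section 6 is therefore not a prohibition, and that part of the objection stands. The conflict with the unqualified dose in 5.2.1 remains.

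**No trial procedure yields an unindexed clearance.** Estimated GFR is scheduled at baseline only (Table 8), in indexed form, so a site would have to convert it by hand. This makes the literal reading less likely in practice. It does not remove the ambiguity, because mL/min is the unit printed.

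**Stronger readings that the text does not support.** A reader might infer that Section 8.3 orders a 25% reduction after hypotension; only stopping is directed, and the reduced restart is optional. A reader might also infer that every small child with normal kidneys would get half the dose. That depends on the unindexed reading, and some of the smallest would have no stated dose instead.

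**Conclusion.** The inconsistency holds. Section 8.3.1 gives an instruction that would lead to a different clofarabine dose from 5.2.1 for any patient in its band. Section 6 does not mention it, and its unit is not the one used for eligibility or for fludarabine. Its reach runs from almost nobody at enrollment (indexed) to many small children with normal indexed GFR (literal). The literal figures rest on CrCl equal to GFR and on the assumed heights and GFR values. The stop-and-restart text in 8.3.8 is likewise missing from Sections 5 and 6.

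The number of patients affected is not established. Section 7.1.4 lists hypotension in more than 20% of patients on clofarabine, and a reader might take this to mean several of the 20. That figure is not limited to hypotension during administration, so the inference does not follow. Nor do the documents show that reductions would lower DLT rates or worsen LFS. No sample size, power or error rate is touched. This is a minor consistency and safety correction.

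**What to change.** Reconcile 8.3.1 and 8.3.8 with 5.2.1 and Section 6 in one of two ways:

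1. State in 5.2.1 or Section 6 whether the renal rule and the hypotension rule apply in this trial and, for the renal rule, which GFR measure is used and whether it is indexed or absolute. If the absolute unit is kept, also say what applies to eligible patients below 30 mL/min.
2. State in Section 8.3 that its dosing text is general product information and does not govern dosing in the trial.

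Which rule applies is for the sponsor's clinicians to decide. The cost is a short paragraph or one sentence, with no extra patients, procedures or analyses.

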## 8.3.2 Form

Clofarabine (1 mg/mL) is supplied in a 20 mL, single-use flint vial. Each vial contains 20 mg clofarabine in 20 mL of solution.

## 8.3.3 Storage and Stability

The pH range of the solution is 4.5 to 7.5. Store at 25°C (77°F); excursions permitted to 15-30°C (59-86°F).

## 8.3.4 Compatibility

In vitro studies suggested that clofarabine undergoes limited metabolism and does not inhibit or induce major CYP enzymes. CYP inhibitors and inducers are unlikely to affect the metabolism of clofarabine. Clofarabine is unlikely to affect the metabolism of CYP substrates. However, no in vivo drug interaction studies have been conducted.

An in vitro transporter study suggested that clofarabine is a substrate of human transporters OAT1, OAT3, and OCT1. A preclinical study using perfused rat kidney demonstrated that the renal excretion of clofarabine was decreased by cimetidine, an inhibitor of the hOCT2. Although the clinical implications of this finding have not been

determined, signs of clofarabine toxicity should be monitored when administered with other hOAT1, hOAT3, hOCT1 and hOCT2 substrates or inhibitors.

## 8.3.5 Handling

Qualified personnel, familiar with procedures that minimize undue exposure to themselves and the environment, should undertake the preparation, handling, and safe disposal of clofarabine in a self-contained and protective environment.

## 8.3.6 Availability

Commercially available. See package insert for further information.

## 8.3.7 Preparation

Filter clofarabine through 0.2 micron syringe filter prior to dilution. Dilute clofarabine with 5% dextrose injection or 0.9% sodium chloride injection to a final concentration of between 0.15 mg/mL and 0.4 mg/mL. The resulting admixture may be stored at room temperature but must be used within 24 hours of preparation.

## 8.3.8 Administration

Infuse over 2 hours. May be infused over 1 hour or per institutional guidelines in some protocols, especially when lower doses are used. Continuous IV fluids are encouraged to decrease adverse events and tumor lysis effects. Consider prophylactic corticosteroids (see Treatment section) to prevent signs/symptoms of capillary leak syndrome or systemic inflammatory response syndrome (SIRS). Hypotension may be a sign of capillary leak syndrome or systemic inflammatory response syndrome (SIRS). Discontinue if the patient becomes hypotensive during administration; may consider therapy re-initiation with 25% dose reduction after return to baseline. An inline filter is not needed for administration. Do not administer any other medications through the same IV line.

Since clofarabine is primarily excreted through the kidneys, drugs with known renal toxicity should be avoided during clofarabine administration. In addition, since the liver is a known target organ for clofarabine toxicity, concomitant use of medications known to induce hepatic toxicity should be avoided.

#### 8.4 Fludarabine

(Fludara®, fludarabine phosphate, 2-fluoro-ara-AMP) NSC# 312887

#### 8.4.1 **Description**

Fludarabine phosphate is a synthetic purine nucleoside. It differs from the physiologic nucleosides, adenosine, in that the sugar moiety is arabinose instead of ribose, and by the addition of a fluorine atom to the purine base adenine. Fludarabine is also a fluorinated

nucleotide analog the antiviral agent vidarabine, (ara-A). The addition of fluorine results in increased aqueous solubility and resistance to enzymatic degradation by adenosine deaminase. Fludarabine (2-fluoro-ara-A) is commercially available as the monophosphate salt (2-fluoro-ara-AMP). The monophosphorylation increases the drug's aqueous solubility while maintaining pharmacologic activity. The chemical name for fludarabine phosphate is 9H-Purin-6-amine, 2-fluoro-9-(5- $\underline{0}$ -phosphono  $\beta$ -D-arabino-furanosyl) (2-fluoro-ara-AMP) and the molecular weight is 365.2.

Fludarabine is a purine antagonist antimetabolite. In vivo, fludarabine phosphate is rapidly dephosphorylated to 2-fluoro-ara-A and then it is phosphorylated intracellularly by deoxycytidine kinase to the active triphosphate, 2-fluoro-ara-ATP. This metabolite appears to act by inhibiting DNA polymerase alpha, ribonucleotide reductase and DNA primase, thus inhibiting DNA synthesis. The mechanism of action of this antimetabolite is not completely characterized and may be multi-faceted.

Phase 1 studies in humans have demonstrated that within several minutes after intravenous infusion, fludarabine phosphate is converted to the active metabolite, 2-fluoro-ara-A and becomes undetectable. Therefore, pharmacokinetics studies have focused on 2-fluoro-ara-A. Fludarabine phosphate 25 mg/m^2 infused intravenously over 30 minutes to adult cancer patients, showed a moderate accumulation of 2-fluoro-ara-A. During a 5-day treatment schedule, 2-fluoro-ara-A plasma trough levels increased by a factor of about 2.

Fludarabine is widely distributed. The volume of distribution at steady state ( $V_{ss}$ ) reported after daily administration of 25 mg/m^2 for 5 days to adults averaged at 96-98 L/m^2. Tissue distribution studies in animals indicate that the highest concentrations of the drug are in liver, kidney, and spleen. Although the extent to which fludarabine and/or its metabolites distribute into the CNS in humans has not been determined to date, severe neurologic toxicity (e.g., blindness, coma) has been reported in patients receiving the drug, particularly in high dosages. There is evidence from animal studies that fludarabine distributes into the CNS and that a toxic metabolite (2-fluoroadenine, possibly formed by bacteria in the GI tract), can be absorbed systematically via enterohepatic circulation and distributed into CSF. According to in vitro data, about 19-29% of fludarabine is bound to plasma proteins.

Following IV administration, fludarabine phosphate is dephosphorylated rapidly to fludarabine. Plasma concentrations of fludarabine decline in a linear, dose-independent manner. The elimination profile of fludarabine also has been reported to be either biphasic or triphasic; however, reported terminal elimination half-lives have been similar. In adult cancer patients receiving fludarabine 25 mg/m^2 as a 30-minute IV infusion daily for 5 days, a terminal half-life of about 20 hours was reported. In a limited number of pediatric patients, the plasma concentration profile of fludarabine exhibited both monoexponential and biexponential decay, with a mean  $t_{1/2}$  of 10.5 hours in patients with monoexponential elimination and a  $t_{1/2}$  of 1.2-1.4 and 12.4-19 hours, respectively, in patients with biexponential elimination.

Renal clearance accounts for about 40% of the total body clearance of fludarabine. Renal elimination appears to become more important at high dosages of the drug. The dose of fludarabine needs to be adjusted in patients with moderate renal impairment.

